1. INTRODUCTION

This statistical analysis plan (SAP) describes the statistical methods for analyzing data for Protocol ALXN2050-NEPH-201, "A Phase 2, Randomized, Double-blind, Placebo-controlled, Dose-finding Study to Evaluate the Efficacy and Safety of ALXN2050 in Adult Participants with Proliferative Lupus Nephritis (LN) or Immunoglobulin A Nephropathy (IgAN)." Standard data presentation instructions and table, figure, and listing specifications are contained in the Data Presentation Plan (DPP) in a separate document.

The objectives of this study are to evaluate the efficacy and safety of oral ALXN2050 compared to placebo, demonstrate proof of concept for efficacy of FD inhibition, and establish a dose in participants with LN or IgAN.

The primary efficacy analysis will be performed for each disease-specific cohort at the end of the 26-week Blinded Initial Evaluation Period after all participants in the disease-specific cohort have completed or withdrawn from the 26-week Blinded Initial Evaluation Period. This analysis will allow for evaluation of the primary endpoint and Phase 3 planning and will have no impact on the progression of this study. The sponsor will be unblinded at this time to conduct the primary analysis. After completion of the 26-week Blinded Initial Evaluation Period, participants in the LN cohort will continue receiving their randomized allocation of study intervention, and both the participants and the investigative site personnel will remain blinded for the remaining 24-week Blinded Extended Treatment Period.

An additional analysis will be performed for each disease-specific cohort at the end of the 24-week Blinded Extended Treatment Period after all participants in the disease-specific cohorts have completed Week 50 or withdrawn from the study.

The final analysis will occur at the end of the 2-year Open-label Extension (OLE) Period after all participants have completed the Safety Follow-up Visit and will include all planned analyses that will be presented in the final clinical study report.

Screening, enrollment, and study intervention have been paused as of 06 Sep 2024. Sensitivity analyses due to dosing pause are added into the relevant sections.

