• In both the LN and IgAN cohorts, data occurring on or after treatment discontinuation will be treated as missing. It is assumed that study participants follow the behavior of their randomized arm. All the missing data will be imputed through multiple imputation (MI) under MAR assumption. Participants with missing data can be modeled based on similar participants with available data if relevant observed factors are accounted for in the model. This MI procedure can be performed in 3 steps: 1) Impute missing data (eg, use PROC MI, *m* times); 2) Analyze each of the *m* complete data sets (eg, use PROC ANCOVA); and 3) Combine results across *K* multiply imputed datasets using Rubin's rule (eg, PROC MIANALYZE).

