4.2.3. Sensitivity Analyses

Table 4 summarizes the sensitivity analyses that will be produced for the primary endpoint.

All sensitivity analyses will be based on an ANCOVA model using the FAS population; in addition sensitivity analysis due to dosing pause will be repeated on PPS population.

Population of no impact by dosing pause will be defined as the participants who have at least one valid 24-hour urine collection obtained within 3 weeks prior to the Week 26 Visit before dosing pause.

Table 4: Sensitivity Analyses

Sensitivity Analysis	Applied Cohorts	Handling of Intercurrent Events/ Description	
Placebo-based multiple imputation + carry-forward	LN cohort only	Treatment discontinuation: Data collected on or after treatment discontinuation will be imputed using placebo-based multiple imputation. Receipt of additional standard of care therapy (LN cohort only): Data collected on or after receipt of additional standard of care therapy will be imputed using the value collected at the time of flare (carry forward).	
Placebo-based multiple imputation	LN and IgAN cohorts	Treatment discontinuation: • Data collected on or after treatment discontinuation will be imputed using placebo-based multiple imputation. Receipt of additional standard of care therapy (LN cohort only): • Data collected on or after receipt of additional standard of care therapy will be imputed using placebo-based multiple imputation.	
Tipping point analysis	LN and IgAN cohorts	Participants who receive additional standard of care therapy (LN cohort only), discontinue treatment, withdraw early, or die are assumed to have outcomes that are worse than otherwise similar participants who remain in the study or did not receive additional standard of care therapy or discontinue treatment.	

Table 4: Sensitivity Analyses

Sensitivity Analysis	Applied Cohorts	Handling of Intercurrent Events/ Description	
Per-randomized stratification analysis	LN and IgAN cohorts	Treatment discontinuation: Data collected on or after treatment discontinuation will be imputed using multiple imputation. Receipt of additional standard of care therapy (LN cohort only): Data collected on or after receipt of additional standard of care therapy will be imputed using the value collected at the time of flare (carry-forward).	

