Sensitivity analysis due to dosing pause- excluding data points impacted by dosing pause	LN and IgAN cohorts	Dosing pause will be regarded as an intercurrent event, in which the analysis is similar to that of treatment discontinuation.	
Sensitivity analysis due to dosing pause- excluding participants impacted by dosing pause	LN and IgAN cohorts	The participants in the population of no impact by dosing pause will be included.	

Abbreviations: IgAN = immunoglobulin A nephropathy; LN = lupus nephritis

Further details of these sensitivity analyses are below.

- Placebo-based multiple imputation + carry-forward: The primary endpoint will be analyzed in the same manner as the primary analysis, except that data collected on or after treatment discontinuation will be assumed missing and imputed using placebobased multiple imputation where it will be assumed that outcomes occurring after treatment discontinuation will follow the trajectory of outcomes similar to the one in the placebo treatment group, taking into account observed values prior to treatment discontinuation (Ratitch, 2014).
- Placebo-based multiple imputation: The primary endpoint will be analyzed in the same manner as the primary analysis, except data collected on or after treatment discontinuation or receipt of additional standard of care therapy (LN cohort only) will be assumed missing and imputed using placebo-based multiple imputation.
- Tipping point analysis: An additional sensitivity analysis will be performed based on the delta-adjusted stress testing method (tipping point analysis). This approach assumes that participants who discontinue from ALXN2050 treatment or who receive additional standard-of-care therapy (for the LN cohort only) experience worsening, defined by a prespecified adjustment (delta) in the primary efficacy endpoint compared with the observed efficacy score of participants who continue the study to the next visit. For each value of delta, the treatment effect will be determined, and the value of delta for which the nominal 2-sided p-value crosses 0.10 will be considered

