4.3.1.4. Complete Renal Response (LN Cohort Only)

Complete renal response (CRR) will be assessed at Weeks 26 and 50. To achieve CRR, participants in the LN cohort must meet all of the following criteria:

- A decrease in mean UPCR to ≤ 0.5 g/g based on two 24-hour urine collections obtained within 2 weeks prior to the study visit (Week 26 or 50)
- eGFR > 60 mL/min/1.73 m² or no eGFR reduction ≥ 20% from the baseline value based on the mean of 2 values. The first eGFR value must be obtained within 2 weeks prior to the study visit (Week 26 or 50) and the second eGFR value will be obtained on the study visit (Week 26 or 50)
- No treatment failure (as defined in Section 4.3.1.10)

The percentage of participants meeting the criteria for CRR as well as individual components of CRR will be summarized at Weeks 26 and 50 by treatment group by calculating the point estimate and 2-sided 95% CI, based on exact confidence limits using the Clopper-Pearson method.

Study participants with treatment discontinuation will be treated as failure to meet CRR criteria and considered nonresponders.

A bar chart will also be provided displaying the proportion of participants meeting the criteria for CRR as well as individual components of CRR at Weeks 26 and 50 by treatment group.

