4.3.2.4. Complete Renal Response (LN Cohort Only)

The endpoint will also be analyzed in the same manner as described in Section 4.3.1.4, except that only the participants in the population of no impact by dosing pause are included.

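### The SAP's no-impact population for the dosing pause is defined by a Week 26 urine collection, so analyses restricted to it also drop participants who left early for unrelated reasons

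*SAP*

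**What the plan says.** The SAP Introduction states: "Screening, enrollment, and study intervention have been paused as of 06 Sep 2024". SAP 4.2.3 therefore adds two pause analyses of the primary endpoint.

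- The first keeps everyone: "Dosing pause will be regarded as an intercurrent event, in which the analysis is similar to that of treatment discontinuation".
- The second is restricted: "The participants in the population of no impact by dosing pause will be included". Membership requires "at least one valid 24-hour urine collection obtained within 3 weeks prior to the Week 26 Visit before dosing pause", and no other criterion is given.

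The section also says "All sensitivity analyses will be based on an ANCOVA model using the FAS population", with the pause analyses repeated on the Per-Protocol Set.

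SAP 4.3.2 reuses the restricted set. Week 50 proteinuria (4.3.2.1) and eGFR (4.3.2.3) get both types of pause analysis. The >30%/>50% reductions (4.3.2.2), CRR (4.3.2.4), PRR (4.3.2.5) and partial remission (4.3.2.6) get only the restricted one. For CRR, the main method applies "except that only the participants in the population of no impact by dosing pause are included".

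The main rules keep early leavers in the analysis. For the primary endpoint (4.2.2), data after treatment discontinuation are set to missing and "All the missing data will be imputed through multiple imputation (MI) under MAR assumption". In LN, the proteinuria value at a renal flare is carried forward once additional standard-of-care therapy is given. For CRR (4.3.1.4), "Study participants with treatment discontinuation will be treated as failure to meet CRR criteria and considered nonresponders". Sections 4.3.1.2, 4.3.1.5 and 4.3.1.13 have the same nonresponder rule.

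**The concern.** An analysis meant to isolate the pause should select participants on the pause. This one selects on having an outcome measurement near Week 26, which is a post-randomisation event. Someone who left for an adverse event or lack of effect months before 06 Sep 2024 is treated as if the pause had removed them.

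For the binary endpoints, the people removed are those whom the main rule counts as failures. Response rates then rise in every arm, and rise most in the arm with the most early leavers. If the result differs from the main analysis, the reader cannot say whether the pause or the removal of leavers caused it, and for these endpoints no second pause analysis can settle the question.

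**Working it through.** The plan states no figure that depends on this definition, so there is none to reproduce. The inputs are the definition (SAP 4.2.3), the main handling rules (4.2.2, 4.3.1), and the planned dropout, arm sizes and geometric means (SAP 5). Leaver, response and flare rates below are assumptions unless stated otherwise.

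**1. Who is in the set**

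| Participant | Main rule | In the set? |
|---|---|---|
| Withdrew at Week 10, well before the pause | Imputed, or nonresponder | No |
| Stopped treatment, kept attending (Protocol 7.1), pre-pause Week 26 collection | Imputed, or nonresponder | Yes |
| On treatment, paused before any Week 26 collection | n/a | No, as intended |
| Pre-pause Week 26 collection, then paused before Week 50 | n/a | Yes, even for Week 50 endpoints |
| LN, only valid collection in the week after the Week 26 Visit, before the pause | Accepted for the primary endpoint (4.2.1) | No |

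A urine collection at an early discontinuation visit does not help the first participant unless that visit falls close to Week 26.

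**2. How many are removed**

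Expected number = dropout × n per arm. IgAN: 0.10 × 24 = 2.4. LN: 0.10 × 30 = 3. These are upper bounds: they need full enrolment, all dropout before the pause, and no leaver with a qualifying collection.

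**3. Binary endpoints**

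If leavers are a share q and all count as nonresponders, a main rate r becomes r/(1 − q) in the restricted set.

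- r = 12/30 = 40.0%, q = 10%: 12/27 = 44.4%.
- r = 40% in both arms, q = 5% versus 15%: 0.40/0.95 = 42.1% versus 0.40/0.85 = 47.1%, a spurious 5-point difference.
- r = 40% in both arms, q = 5% versus 20%: 42.1% versus 0.40/0.80 = 50.0%, a spurious 7.9 points.
- Equal q in both arms with equal r: no spurious difference, only inflated rates.

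**4. Primary endpoint, IgAN**

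The imputation model (SAP 6.4.3) uses treatment, baseline and stratum, the same covariates as the ANCOVA. Imputed and observed-only analyses should therefore nearly agree. In 300 simulated two-arm trials (24 per arm, geometric mean ratios to baseline of 0.55 and 0.85, 10% missing at random) they did: mean estimates −0.4132 versus −0.4131, standard errors 0.178 versus 0.177, mean absolute difference 0.003 on the log scale.

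**5. Primary endpoint, LN**

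Participants who flare and then leave lose their carried-forward value. Let f1 and f0 be their shares on 180 mg and placebo, c their carried-forward ratio to baseline, and let the planned 0.40 and 0.60 hold for everyone else:

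ln GMR = [(1 − f1) ln 0.40 + f1 ln c] − [(1 − f0) ln 0.60 + f0 ln c]

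- f1 = f0 = 0.10: 0.9 × ln(0.40/0.60) = −0.365, GMR 0.694. With those participants removed: 0.40/0.60 = 0.667.
- f1 = 1/30, f0 = 3/30, c = 1.75: GMR 0.629. With those participants removed: 0.667.

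The shift can go either way.

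**6. Week 50 reuse**

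Planned Day 183 is first dose + 182 days and planned Day 351 is first dose + 350 days. Planned Day 183 precedes 06 Sep 2024 for first doses up to 7 Mar 2024; planned Day 351 does so only up to 21 Sep 2023. On schedule, participants first dosed from 22 Sep 2023 to 7 Mar 2024 reach Week 26 before the pause but not Week 50, yet they can count as unaffected in the Week 50 analyses.

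**The case against.** The strongest reply is that the damage is narrow. For the primary endpoint, Week 50 proteinuria and eGFR, the intercurrent-event version of the pause analysis retains early leavers, so the reader has a comparison. Stoppers who continue visits also remain, still handled as imputed or nonresponders. A reader might infer that every pause sensitivity analysis becomes a completer analysis, or that everyone who stopped early is removed; the documents support neither. All of this stands and limits the point to the restricted-set analyses.

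Second, the figures are bounds or illustrations. Enrolment was itself paused, and the documents give no actual enrolment or dropout by the pause date. Secondary analyses are descriptive, and the exact 95% intervals are wide: 22.7% to 59.4% for 12/30 and 25.5% to 64.7% for 12/27. That stands as to size. It does not answer the objection that the set fails to match its label.

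Third, SAP 6.1.8, 6.1.10 and 6.1.11 treat CRR, partial remission and PRR as missing when both collections are missing, which sits uneasily with the nonresponder rule. If the missing rule prevailed for leavers, they would already be outside the main denominator and the inflation for those three endpoints would disappear. The SAP does not reconcile the two. The binary arithmetic above assumes that the nonresponder rule, stated in the endpoint sections for treatment discontinuation, governs.

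Fourth, the LN week-after window is an edge case. Collections are scheduled before the visit and one suffices, so it matters only when none was valid.

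**Conclusion.** The concern holds for analyses restricted to the no-impact population. The definition excludes participants who left, or gave no Week 26 collection, for reasons unrelated to the pause. It matters most for the >30%/>50% reductions, CRR, PRR and partial remission, which have no other pause analysis. Response rates could rise by about 4 points from 40% at the planned dropout (upper bound), and unequal leaving could create a difference of about 5 points under the assumed 5% versus 15%. In LN, lost carried-forward values can move the primary ratio in either direction, under assumed flare rates. For the IgAN primary endpoint the effect is negligible.

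Reuse of a Week 26 criterion for Week 50 endpoints is a further mismatch, because participants paused in between are labelled unaffected. A reader might also infer that the primary result is compromised; it is not, since the main FAS analyses do not use this set.

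**What to change.** In SAP 4.2.3, define the set by a date fixed at first dose:

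- Week 26 endpoints: participants whose planned Day 183 (first dose date + 182 days) falls before 06 Sep 2024.
- Week 50 endpoints: participants whose planned Day 351 (first dose date + 350 days) falls before 06 Sep 2024.

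Include them whether or not they reached the visit, and apply the planned rules inside the set: multiple imputation, carry-forward and nonresponder. State whether the nonresponder rule or the both-collections-missing rule takes precedence for participants who discontinued. Membership then no longer depends on a collection, so the LN window gap closes as well.

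The cost is a short edit to 4.2.3 with a matching reference in 4.3.2, and no new data. The Week 50 set will be smaller. A few participants near the cut-off may be misclassified, because visits may fall 5 days (Week 26) or 7 days (Week 50) either side of the planned day and collections precede the visit.

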8.1.1.2. IgAN Cohort

Participants in the IgAN cohort will be required to provide 2 separate, complete, and valid 24-hour urine collections during the Screening Period (to assess eligibility). For evaluation of the primary and key secondary endpoints, the two 24-hour urine collections should be obtained within 2 weeks before the Week 26 and Week 50 Visits. Additional 24-hour urine collection is also scheduled for Week 102 and Week 154.

Hence, a 24-hour urine collection is considered valid if all the following criteria are met, otherwise the urine collection is required to be repeated:

- The collection is between 22 to 26 hours in duration (ie, time from the initial discarded void to the last void/attempt to void).
- No voids are missed between the start and end time of the collection as indicated by the participant's urine collection diary.

Urine collections will be reviewed by the Medical Monitoring team.

Inadequate collections may need to be repeated as soon as possible within the time frames outlined in the SoA (Section 1.3) in order to ensure that 2 valid collections are obtained for each of the study time points.

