4.2.1. Derivation of Endpoint(s)

The primary endpoint for the study is percentage change from baseline to Week 26 in proteinuria based on 24-hour urine collection(s) at each time point.

Proteinuria will be measured by absolute urine protein (UP) in g/day as well as by urine protein-to-creatinine ratio (UPCR) in g/g for each disease cohort as follows:

- For the LN cohort, proteinuria measured by UPCR as well as by UP is derived from a single 24-hour urine collection at Screening and the mean of 2 separate 24-hour urine collections within 3 weeks prior to or 1 week after Week 26 Visit to assess the primary endpoint. Two separate 24-hour collections should be obtained at Week 50 Visit to assess the secondary endpoint, as long as they are collected within 3 weeks prior to Week 50 Visit. Additional 24-hour urine collections are also scheduled for Weeks 102 and 154.
- For the IgAN cohort, proteinuria measured by UP as well as UPCR is derived from the mean of 2 valid 24-hour urine collections during the Screening Period and within 3 weeks prior to Week 26 Visit to assess the primary endpoint. Two separate 24-hour collections should be obtained at Week 50 Visit to assess the secondary endpoint, as long as they are collected within 3 weeks prior to or 1 week after Week 50 Visit. Additional 24-hour urine collections are also scheduled for Weeks 102 and 154.

For the primary endpoint, proteinuria will be based on UPCR for the LN cohort and UP for the IgAN cohort. For both cohorts, the natural logarithm will be used to transform proteinuria values before the analysis to reduce skewness. When 2 valid 24-hour urine collections are required and only 1 valid collection is available at the visit, then this value will be used for analysis.

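### In the analysis that excludes participants affected by the dosing pause, no rule keeps a post-pause urine collection out of the Week 26 mean, and its LN window is narrower than the endpoint's

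*SAP*

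**What the plan says.** **The pause.** The SAP Introduction records that "Screening, enrollment, and study intervention have been paused as of 06 Sep 2024".

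**The outcome (SAP 4.2.1).** For LN, the Week 26 value is the "mean of 2 separate 24-hour urine collections within 3 weeks prior to or 1 week after Week 26 Visit". For IgAN, proteinuria comes from "the mean of 2 valid 24-hour urine collections during the Screening Period and within 3 weeks prior to Week 26 Visit". There is a fallback: if two collections are required and "only 1 valid collection is available at the visit, then this value will be used for analysis".

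**The population (SAP 4.2.3).** Being unaffected by the pause means having "at least one valid 24-hour urine collection obtained within 3 weeks prior to the Week 26 Visit before dosing pause". The same wording serves both cohorts.

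**The analyses (SAP 4.2.3, Table 4).** Two rows deal with the pause. One treats it as an intercurrent event, handled like treatment discontinuation. The other only selects people: "The participants in the population of no impact by dosing pause will be included". The text under the table describes this second one as a subgroup analysis and adds no rule about which collections are averaged.

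**The concern.** The population rule and the endpoint rule do not fit together for a participant with one collection before 06 Sep 2024 and one after. That participant counts as unaffected, yet half of the averaged Week 26 value comes from urine passed after dosing stopped. In an active arm, this can pull the estimate toward no difference in the very analysis meant to be free of the pause.

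The second mismatch runs the other way. The LN endpoint window extends one week past the visit, while the population rule stops at the visit. An LN participant can thus have a valid on-drug Week 26 value and still be left out.

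The population is used again for the Per-Protocol repeat (SAP 4.2.3) and for the key secondary endpoints (SAP 4.3.2). Several of those are threshold responses, for which a mixed mean could change one person's responder status.

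**Working it through.** The plan states no figure on this point, so there is none to reproduce. The check has two parts: whether any rule closes the gap, and how large the effect could be.

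**Does another rule remove the post-pause collection?**
- *The single-collection fallback (SAP 4.2.1).* It applies only when the second valid collection is unavailable. In Protocol 8.1.1.2, "a 24-hour urine collection is considered valid if all the following criteria are met", and those criteria are a duration of 22 to 26 hours and no missed voids. Dosing status is not one of them, so a post-pause collection can be valid and available.
- *The primary intercurrent events (SAP 1.1 and Table 3).* These are additional standard of care (LN) and treatment discontinuation. SAP 4.1.4 lists the dosing pause as a separate item, so the discontinuation rule does not clearly reach it.
- *The companion pause analysis.* It handles the pause like discontinuation, after which data are treated as missing (SAP 4.2.2). Combined with the fallback, this leaves the pre-pause collection alone. That rule belongs to the companion row and is not carried into the participant-selection row.

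No rule in the participant-selection analysis closes the gap.

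**Size for one straddling active participant.** Inputs are the assumed 26-week-to-baseline ratios in SAP section 5: placebo 0.85 and active 0.55 (IgAN); 0.60 and 0.40 (LN). The active-to-placebo ratio is g = 0.55/0.85 = 0.647 (IgAN) and g = 0.40/0.60 = 0.667 (LN). If a fraction r of the log effect has reverted by the second collection, that collection has ratio g^(1−r). The mean of the two is m = [g + g^(1−r)]/2, and the share of the log effect lost is 1 − log(m)/log(g). The documents do not give r, so a range is shown.

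| r | IgAN m | IgAN share lost | LN m | LN share lost |
|---|---|---|---|---|
| 25% | 0.684 | 12.8% | 0.702 | 12.8% |
| 50% | 0.726 | 26.4% | 0.742 | 26.3% |
| 100% | 0.824 | 55.4% | 0.833 | 55.0% |

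**How many straddle.** Only participants for whom the pause falls between their two collections matter. The accrual pattern and the gap between collections are not in the documents. Assume Week 26 visits spread evenly over A weeks. The expected number is then (participants/A) × gap in weeks, for the 180 mg and placebo arms together:
- IgAN (48): 48/130 × 1 = 0.4 to 48/78 × 2 = 1.2, for gaps of 7 to 14 days and A from 130 down to 78.
- LN (60): 60/130 × 1 = 0.5 to 60/78 × 2 = 1.5.
- At the widest gap the windows allow, with A = 78: IgAN 48/78 × 3 = 1.8; LN 60/78 × 4 = 3.1.

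About half of these would be on placebo, where there is no drug effect to lose.

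**Group level.** If 5% of the 180 mg arm straddles (24 × 0.05 = 1.2 people in IgAN, 30 × 0.05 = 1.5 in LN) with full reversion, the log effect becomes 0.435 × (1 − 0.05 × 0.554) = 0.423 in IgAN, and the geometric mean ratio moves from 0.647 to 0.655. In LN, 0.405 × (1 − 0.05 × 0.550) = 0.394, and the ratio moves from 0.667 to 0.674.

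**LN window.** Wrongful exclusion needs an LN participant with no usable pre-pause collection in the three weeks before the visit and a usable one, still before the pause, in the week after. Protocol 8.1.1.1 schedules both collections in the two weeks before the visit, so this should be uncommon. The documents allow no count.

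**The case against.** The best defence is that the plan already has the needed analysis. The companion row of Table 4 handles the pause as an intercurrent event and can reasonably be read as keeping a straddler's pre-pause urine and discarding the rest. This stands, with two limits: it is a reading and not an explicit rule, and it leaves the other row as it is. The two rows may then differ partly because they treat the same participant differently.

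A second defence is that the one-collection threshold is sensible, since 4.2.1 itself accepts a single value. This also stands. A reader might infer that the threshold is the error and that two pre-pause collections should be required. The documents do not support that: requiring two would discard usable on-drug outcomes. What is missing is a statement of which collections are averaged.

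Third, the effect is small. At 5% straddling and full reversion the ratio moves by less than 0.01, against an assumed SD of 0.60 on the log scale. The 55% figure is a worst case for one participant, because nothing in the documents shows that the drug effect vanishes between collections. This stands as a limit on importance. It does not make the rule consistent.

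**Conclusion.** The inconsistency is real, conditional and minor. As written, off-drug urine can stay in the outcome of active-arm participants whose two collections straddle the pause, and an unaffected LN participant can be dropped.

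A reader might go further and infer that the plan as a whole cannot show whether the pause changed the result, or that this sensitivity analysis is materially biased. Neither follows. The companion analysis exists, the primary estimand does not depend on this population, and the expected number of straddlers is probably about one per cohort or fewer. Any bias would be toward no difference. For the LN exclusion, the visible cost is a little precision; no bias is shown.

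These sizes rest on the SAP's planning ratios, an assumed range of reversion, the planned arm sizes, even accrual over 78 to 130 weeks and a gap of 7 to 14 days. Faster accrual before the pause or wider gaps would raise the count. The actual number can be read from collection dates without unblinding.

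**What to change.** In SAP 4.2.3:
- Keep the criterion of at least one valid pre-pause collection.
- State that, in this analysis, only collections obtained before the dosing pause are used to derive the Week 26 value, a single value being acceptable under 4.2.1.
- Replace the common three-week window with the cohort-specific one in 4.2.1: LN from three weeks before to one week after the visit, IgAN the three weeks before it.

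This takes a sentence or two and no new data. The cost is slightly more noise for the few participants whose value then rests on one collection.
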